APPENDIX B – CLINICAL GLOBAL IMPRESSION -GLOBAL IMPROVEMENT (CGI-I) SCALE

Clinical Global Impression – Global Improvement (CGI –I) Scale
 
Rate total improvement whether or not, in your clinical judgment, it is due entirely to drug treatment.
 
Compared to his/her condition at baseline, how much has he/she changed?
 
 0 = Not assessed
 
 1 = Very much improved
 
 2 = Much improved
 
 3 = Minimally improved
 
 4 = No change
 
 5 = Minimally worse
 
 6 = Much worse
 
 7 = Very much worse

--

APPENDIX C – PATIENT GLOBAL IMPRESSION OF CHANGE (PGIC) SCALE

PATIENT GLOBAL IMPRESSION OF CHANGE
 
Since the start of the study, the subject reports their overall status as: (check one box only)
 
 Very Much Worse
 
 Much Worse
 
 Minimally Worse
 
 No Change
 
 Minimally Improved
 
 Much Improved
 
 Very Much Improved

APPENDIX D – EXAMPLES OF DIARY COLLECTION TOOLS
Response to Study Device Form

Day 1 - Day _____

Subject #: _____ - _____ **Subject Initials:** _____

Instructions: Enter the date as instructed by your study investigator and select the one number that best indicates the average intensity of pain you have had over the last 24 hours in the area you are treating.

Day 1 - Date: _____

Pain Intensity Assessment (NPRS) Questionnaire										
										
0	1	2	3	4	5	6	7	8	9	10
No Pain										Worst Pain Imaginable

Day 2 - Date: _____

Pain Intensity Assessment (NPRS) Questionnaire										
										
0	1	2	3	4	5	6	7	8	9	10
No Pain										Worst Pain Imaginable

Day 3 - Date: _____

Pain Intensity Assessment (NPRS) Questionnaire										
										
0	1	2	3	4	5	6	7	8	9	10
No Pain										Worst Pain Imaginable

Day 4 - Date: _____

Pain Intensity Assessment (NPRS) Questionnaire										
										
0	1	2	3	4	5	6	7	8	9	10
No Pain										Worst Pain Imaginable

Day 5 - Date: _____

Pain Intensity Assessment (NPRS) Questionnaire										
										
0	1	2	3	4	5	6	7	8	9	10
No Pain										Worst Pain Imaginable

Day 6 - Date: _____

Pain Intensity Assessment (NPRS) Questionnaire										
										
0	1	2	3	4	5	6	7	8	9	10
No Pain										Worst Pain Imaginable

Day ___ Date: _____

Pain Intensity Assessment (NPRS) Questionnaire										
										
0	1	2	3	4	5	6	7	8	9	10
No Pain										Worst Pain Imaginable

Day ___ Date: _____

Pain Intensity Assessment (NPRS) Questionnaire										
										
0	1	2	3	4	5	6	7	8	9	10
No Pain										Worst Pain Imaginable

Day ___ Date: _____

Pain Intensity Assessment (NPRS) Questionnaire										
										
0	1	2	3	4	5	6	7	8	9	10
No Pain										Worst Pain Imaginable

Day ___ Date: _____

Pain Intensity Assessment (NPRS) Questionnaire										
										
0	1	2	3	4	5	6	7	8	9	10
No Pain										Worst Pain Imaginable

Day ___ Date: _____

Pain Intensity Assessment (NPRS) Questionnaire										
										
0	1	2	3	4	5	6	7	8	9	10
No Pain										Worst Pain Imaginable

Day ___ Date: _____

Pain Intensity Assessment (NPRS) Questionnaire										
										
0	1	2	3	4	5	6	7	8	9	10
No Pain										Worst Pain Imaginable

Day ___ Date: _____

Pain Intensity Assessment (NPRS) Questionnaire										
										
0	1	2	3	4	5	6	7	8	9	10
No Pain										Worst Pain Imaginable

You have completed your Day 1 - Day ___ Forms. Please return this packet to the clinic staff at your next Visit.

Medication Consumption

Day 1 - Day _____

Subject #: _____ - _____ Subject Initials: _____

Instructions: Enter the date as instructed by your study investigator and list the medication(s) taken for your pain in the provided field(s) along with the number of pills you have taken over the last 24 hours.

Day 1 - Date: _____

Medication Name:		Number of Pills Taken:	
Medication Name:		Number of Pills Taken:	
Medication Name:		Number of Pills Taken:	

Day 2 - Date: _____

Medication Name:		Number of Pills Taken:	
Medication Name:		Number of Pills Taken:	
Medication Name:		Number of Pills Taken:	

Day 3 - Date: _____

Medication Name:		Number of Pills Taken:	
Medication Name:		Number of Pills Taken:	
Medication Name:		Number of Pills Taken:	

Day 4 - Date: _____

Medication Name:		Number of Pills Taken:	
Medication Name:		Number of Pills Taken:	
Medication Name:		Number of Pills Taken:	

Day ____ - Date: _____

Medication Name:		Number of Pills Taken:	
Medication Name:		Number of Pills Taken:	
Medication Name:		Number of Pills Taken:	

Day ____ - Date: _____

Medication Name:		Number of Pills Taken:	
Medication Name:		Number of Pills Taken:	
Medication Name:		Number of Pills Taken:	

Day ____ - Date: _____

Medication Name:		Number of Pills Taken:	
Medication Name:		Number of Pills Taken:	
Medication Name:		Number of Pills Taken:	

Day ____ - Date: _____

Medication Name:		Number of Pills Taken:	
Medication Name:		Number of Pills Taken:	
Medication Name:		Number of Pills Taken:	

Day ____ - Date: _____

Medication Name:		Number of Pills Taken:	
Medication Name:		Number of Pills Taken:	
Medication Name:		Number of Pills Taken:	

Day ____ - Date: _____

Medication Name:		Number of Pills Taken:	
Medication Name:		Number of Pills Taken:	
Medication Name:		Number of Pills Taken:

## 1. LIST OF ABBREVIATIONS

Abbreviation	Explanation
AE	Adverse Event
ABI	Ankle-Brachial Index
BMI	Body Mass Index
CFR	Code of Federal Regulations
CRA	Clinical Research Assistant / Associate
CSR	Clinical Study Report
EDC	Electronic Data Capture
FCC	Federal Communication Commission
FDA	Food & Drug Administration
IQR	Inter-Quartile Range
IRB	Institutional Review Board
LSA	Laser Sensor Assembly
MedDRA	Medical Dictionary for Regulatory Activities
NCV	Nerve Conduction Velocity
PEMF	Pulsed Electromagnetic Field
PPDN	Painful Peripheral Diabetic Neuropathy
PRFE	Pulsed Radio Frequency Energy
PRN	As Needed
QA	Quality Assurance
QC	Quality Control
SAE	Serious Adverse Event
SAP	Statistical Analysis Plan
SAS	Statistical Analysis System
SMET	Submaximal Effort Tourniquet Test
SPP	Skin Perfusion Pressure
SSR	Sympathetic Skin Response
TMF	Trial Master File

## 2. INTRODUCTION

The purpose of this Statistical Analysis Plan (SAP) is to prospectively outline the types of analyses and presentations of the data that will form the basis for conclusions regarding this clinical investigation. The analyses defined in this plan should answer the safety and effectiveness objectives outlined in the protocol, and explain in detail how the data will be handled or analyzed, adhering to commonly accepted standards and practices of biostatistical analysis in the medical device industry.

This document contains information to support the generation of a Clinical Study Report (CSR) for Clinical Protocol RBI.2015.005, including detailed descriptions of the statistical methods to be applied, as well as the analysis summary tables and figures and subject data listings intended to present the analysis results.

Provant is a medical device manufactured by Regenesis Biomedical, Inc. (Scottsdale, AZ), that has been cleared by the FDA (K972093, K091791, and K131979) for adjunctive use in the palliative treatment of post-operative pain and edema of soft tissue. The device delivers self-administered, non-thermal, non-ionizing pulsed electromagnetic energy to the target tissue, using 27.12 MHz pulses lasting 42 microseconds and delivered 1000 times per second. The system generates an electromagnetic field that is continuously monitored and regulated to ensure consistent dosing. The therapeutic electromagnetic field is delivered by means of an applicator pad that is placed against the treatment site. The device is non-invasive and does not require placement of surface or deep electrodes, nor removal of bandages or clothing.

The planned analyses identified in this SAP may be included in regulatory submissions, medical presentations and manuscripts. Exploratory analyses, not identified in this SAP, may be performed to support the clinical development program. Any post-hoc or unplanned analyses that are performed but not identified in this SAP will be clearly identified in the CSR. The structure and content of this SAP provides sufficient detail to meet the requirements identified by the FDA and the International Conference on Harmonization (ICH) Guidance on Statistical Principles for Clinical Trials.

### **3. STUDY OBJECTIVES AND ENDPOINTS**

#### **3.1. Study Objectives**

The primary objective of this study is to obtain data on the safety and effectiveness of PEMF treatment in patients with various pain etiologies. Data from enrolled patients will contribute to a patient registry on the post-market use of Provant.

This study will determine the extent to which Pulsed Electromagnetic Field (PEMF) therapy contributes to the management of various pain etiologies in a real-world setting.

#### **3.2. Endpoints and Study Assessments**

##### **3.2.1. Baseline Assessments**

#### **Outcome Assessments**

Outcome measures used as part of the standard practice regimen

##### **Pain Sensation**

- Dull Pressure
- Ache
- Spasm
- Sharp
- Sting
- Burning
- Shooting
- Stabbing
- Squeezing
- Bloating
- Cramping
- Trying
- Exhausting
- Depressing
- Annoying
- Aggravating
- Punishing
- Tolerable
- Unrelenting
- Intolerable

Pain Radiation (yes or no; if yes, the location is added as a verbatim field)

Pain Intensity Assessment (0-10 scale)

Temporal/Timing

- Constant
- Unprovoked

- Wax/Wanes
- Intermittent
- Onset: Sudden or Gradual

Aggravates or Worsens the Pain

- Walking/Running
- Stooping
- Flexing
- Extending
- Pivoting
- Deep Massage
- Exercise/Movement/ Exertion
- Reclining
- Bending
- Sitting
- Lifting
- Medication (specific medications will be included in a listing)
- Energy Based (specific information will be included in a listing)
- Carrying
- Chewing
- Talking
- Lights/Flashing
- Noise/Sound
- Smells
- Motion
- Heat
- Cold
- Light Touch

Alleviates or Reduces the Pain – Medications

- Opioid
- Antidepressant
- Anticonvulsant
- Serotonin Inhibitor (SSRI)
- Anesthetic
- NSAID
- Other (specific information will be included in a listing)

Topical Agents and Medications

- Anesthetic
- Counter Irritant
- Capsaicin
- Other (specific information will be included in a listing)

Energetic Therapy:

- Provant
- Other PEMF
- TENS
- Acupuncture
- US
- Light Therapy
- Infrared
- PUVA
- Other (specific information will be included in a listing)

#### Adjunctive Therapy

- Massage
- Heat
- Cold
- Exercise/Movement
- Rest/Relaxation
- Dietary
- Compression/Stockings
- Behavior Feedback
- Other (specific information will be included in a listing)

#### **Baseline Edema Assessment**

Edema Evaluation at treatment site

- Amount: Mild, Moderate, Severe
- Pitting: Non-pitting, 1+, 2+, 3+, 4+, Lymphedema

#### **Baseline Wound Assessment**

Total number of wounds (actual number will be tabulated)

Wound Assessment:

- Postoperative
- Laminectomy
- Post-Surgical Debridement
- S/P Surgical Revision
- Post Procedure
- Thoracotomy
- S/P Amputation
- Joint Replacement
- Joint Revision
- Other (specific information will be included in a listing)

#### Amputation Site

- TMA
- BKA
- AKA
- Forearm

- Upper Arm
- Other (specific information will be included in a listing)

### **Provant Treatment Regimen**

Frequency of Treatment:

- Q.D. (every day)
- B.I.D (twice daily)
- PRN (as needed)
- Other (specific information will be included in a listing)

Length of individual Treatment Session:

- 30 minutes (default)
- 15 minutes
- 1 hour (two 30 minute sessions)
- Other (specific information will be included in a listing)

Weight

### **3.2.2. Interim and End of Treatment Visit Assessments**

#### **Outcome Assessments**

Outcome measures used as part of the standard practice regimen

#### **Pain Intensity Assessment (Average)**

Single pain score of the average intensity over the past 7 days

#### **Assessment of Compliance and DC packs**

##### **Compliance (Yes or No)**

##### **Total number of pack provided**

##### **Provant Device Return (End of Treatment Visit)**

Edema Evaluation at treatment site

- Mild, Moderate, Severe
- Pitting: Non-pitting, 1+, 2+, 3+, 4+, Lymphedema

Weight (End of Treatment Visit)

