Thirty subjects in this study were evaluated for the effectiveness of the Provant Therapy System in the treatment of post-surgical pain after back surgery. Provant treatment twice daily for 45 days was associated with improved pain scores, improved overall well-being, improved physical function, and reduced analgesic consumption, especially in subjects who had undergone a discectomy.

The purpose of the current study is to confirm the findings of pain relief observed in patients receiving treatment with Provant in a “real-world”, post-market setting. Data from this study may be combined with other studies conducted in the post-market setting, i.e., in a patient registry.

II. STUDY OBJECTIVES

This study is designed to provide post-market evidence of the safety and effectiveness of the Provant Therapy System for improving pain and edema in subjects with multiple pain etiologies.

III. STUDY DESIGN

A. Study Design

The study is an open-label, non-controlled study of the safety and effectiveness of investigator determined Provant therapy in subjects with pain and/or edema from various pain etiologies.

B. Efficacy Assessments

Outcome measures of response to treatment with Provant will be determined based on the location of the subject's treatment area. Protocol required assessments will include baseline and interim / end of treatment visit and 3-month follow-up (post-treatment) pain scores using an 11-point numeric pain rating scale (NPRS), and a Clinical Global Impression – Global Improvement (CGI-I) Scale and a Patient Global Impression of Change (PGIC) Scale. All outcome measures used in the investigator's standard of practice are non-invasive assessments, e.g., pain scores, SF-36, ankle-foot scales, oxygen perfusion (MOXY), and diaries with some subjects.

C. Safety Evaluation

All observed and reported adverse effects will be recorded by the research staff. Start dates, end dates, frequency, severity of the event, any treatment required to treat the event, and the investigator's judgment on causality and relationship to the device will be assessed for each AE. Any AE occurring after the signing of the informed consent form will be recorded. Only those AEs occurring after initiation of the first treatment with the study device will be considered treatment-emergent AEs.

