### **7.2. Handling of Dropouts or Missing Data**

Missing data may have an impact upon the interpretation of the trial data. Values for missing data will not be imputed, however a tabulation of the last recorded observations will be performed. All available data for subjects who do not complete the study will be included in data listings.

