### 10.3. End of Study Assessments

#### 10.3.1. Description of the Data for Analysis

The last intra-subject data collected from the Outcome Assessments, Pain Intensity Assessment (Average), and Edema Assessment will be summarized. Results will be summarized in the following tables. Continuous variables will be summarized using descriptive statistics; categorical variables will be summarized using counts and percentages. Results will be presented using the Level 2 displays.

Table 14.4.2.1 Summary of the Final Outcome Assessments (ITT / Safety Population)

Table 14.4.2.2 Summary of the Final Pain Intensity Assessment (ITT / Safety Population)

Table 14.4.2.3 Summary of the Final Edema Assessments (ITT / Safety Population)

The supportive data for these tables will be presented in Listing 16.2.9 entitled *Outcome Assessment*; Listing 16.2.10 entitled *Pain Intensity Assessment*; Listing 16.2.11 entitled *Final Edema Assessment*; These listings will be sorted by subject and relative day the measurements were recorded.

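### The edema items, as the SAP specifies them, have no 'none' or 'resolved' level at any visit, so complete resolution cannot be recorded and edema benefit is understated

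*SAP*

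**What the plan says.** SAP 3.2.1, Baseline Edema Assessment, grades edema at the treatment site as "Amount: Mild, Moderate, Severe". SAP 3.2.2 repeats the three levels for later visits: "Mild, Moderate, Severe". Both sections carry the same second item, "Pitting: Non-pitting, 1+, 2+, 3+, 4+, Lymphedema". Neither asks whether edema is present. In SAP 3.2.2 the list is printed under the device-return sub-heading, which is tagged to the End of Treatment Visit. SAP 10.2.1 also plans an interim edema table, and the SAP has no other follow-up edema list, so I take the same levels to apply at interim visits.

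Protocol Section II states the effectiveness objective as "improving pain and edema in subjects with multiple pain etiologies". SAP 10.2.1 and 10.3.1 give edema its own tables, 14.4.1.3 (interim) and 14.4.2.3 (final), with categorical variables shown as counts and percentages.

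Two rules decide what happens to a blank. SAP 10.3.1: "The last intra-subject data collected from the Outcome Assessments, Pain Intensity Assessment (Average), and Edema Assessment will be summarized". SAP 7.2: "Values for missing data will not be imputed, however a tabulation of the last recorded observations will be performed".

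**The concern.** The best edema outcome has no code. A subject who enters with edema and leaves without it fits none of the printed levels, so the site has to choose an entry that says something else. Whichever it chooses, the subject who did best looks no better than one with residual mild edema, disappears from the table, or appears under an older and worse grade.

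At stake is the edema part of the Section II objective. Subjects may be enrolled for edema alone (Protocol III.D, inclusion criterion 2), and the SAP's Level 2 display has a column for them. A resolution that was never recorded cannot be reliably recovered at analysis.

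**Working it through.** **1. Is absence recordable anywhere in the edema items?**

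| Item | Baseline (SAP 3.2.1) | Follow-up (SAP 3.2.2) | Level meaning absent |
|---|---|---|---|
| Amount | mild, moderate, severe | mild, moderate, severe | none |
| Pitting | non-pitting, 1+ to 4+, lymphedema | same | none |
| Edema present, yes/no | not listed | not listed | – |

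'Non-pitting' describes a type of edema, so it cannot stand for absence. SAP 7 shows unknown and not-performed entries apart from missing ones, but neither status means resolved. Other items in the same documents can record absence: the diary pain scale has a zero anchor (Protocol Appendix D), pain radiation is yes/no and wounds are counted (SAP 3.2.1), and action taken for an adverse event includes 'None' (SAP 3.2.3).

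**2. What happens to a resolved case?**

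- Route A, entered as Mild. Mild-to-none shows as no change, and moderate- or severe-to-none shows only a partial improvement.
- Route B, left blank with no earlier follow-up grade. With no imputation, the subject leaves Table 14.4.2.3.
- Route C, left blank with an earlier grade on file. Under SAP 10.3.1 the earlier grade becomes the final result.

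**3. Direction of the error.** The plan gives no edema figure to reproduce, and no resolution rate or baseline distribution. All inputs here are assumptions: 100 subjects with edema at baseline (30 mild, 40 moderate, 30 severe); a fraction r of each grade resolves fully; 20% of unresolved moderate or severe cases improve by one level. In route C the earlier grade is assumed equal to baseline.

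One-level improvers = 0.20 × (40 + 30) × (1 − r) = 14(1 − r).

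- True number improved = 100r + 14(1 − r), out of 100
- Route A = 70r + 14(1 − r), out of 100 (the 30r mild cases that resolve are lost)
- Route B = 14(1 − r), out of 100(1 − r), which is 14.0% at any r
- Route C = 14(1 − r), out of 100

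| r | True | A: as Mild | B: blank, dropped | C: earlier grade stands |
|---|---|---|---|---|
| 10% | 10 + 12.6 = 22.6% | 7 + 12.6 = 19.6% | 12.6/90 = 14.0% | 12.6% |
| 20% | 20 + 11.2 = 31.2% | 14 + 11.2 = 25.2% | 11.2/80 = 14.0% | 11.2% |
| 40% | 40 + 8.4 = 48.4% | 28 + 8.4 = 36.4% | 8.4/60 = 14.0% | 8.4% |

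**4. The same example in the form SAP 10.3.1 plans (percent per level, r = 20%).** Unresolved: 24 mild, 32 moderate, 24 severe. One-level moves: 0.20 × 32 = 6.4 from moderate to mild and 0.20 × 24 = 4.8 from severe to moderate. This leaves mild 24 + 6.4 = 30.4, moderate 32 − 6.4 + 4.8 = 30.4, severe 24 − 4.8 = 19.2, and 20 resolved (6 from mild, 8 from moderate, 6 from severe).

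| Level | True | A | B (n = 80) | C |
|---|---|---|---|---|
| None | 20.0 | no row | no row | no row |
| Mild | 30.4 | 30.4 + 20 = 50.4 | 30.4/80 = 38.0 | 30.4 + 6 = 36.4 |
| Moderate | 30.4 | 30.4 | 30.4/80 = 38.0 | 30.4 + 8 = 38.4 |
| Severe | 19.2 | 19.2 | 19.2/80 = 24.0 | 19.2 + 6 = 25.2 |

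All three routes understate the benefit. In B the recorded result does not respond to the resolution rate. In C it falls as true resolution rises.

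**The case against.** The strongest reply is that the case report form is not in the documents. SAP 3.2 may not list every box on the form: SAP 7 refers to unknown and not-performed entries, yet neither appears in the edema lists. That stands, and it is why the form has to be checked first and why confidence is moderate. It does not rescue the SAP text, which would still need a rule for a level it does not list.

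A second reply is that benefit can show elsewhere. The protocol-required measures are the NPRS, CGI-I and PGIC, and the two global scales allow an edema subject to be rated very much improved. The protocol also lets sites use outcome measures suited to the pain or edema treated, and these would feed Table 14.4.2.1. This mitigates the problem, but the global scales are not edema-specific, no edema measure is named among the site-chosen ones, and neither repairs the edema tables.

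Third, the study is single-arm and descriptive, with no formal hypothesis test and no formal basis for its sample size. The error works against the device, so it does not create a false claim of effectiveness. This also stands and lowers the severity.

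Two further complaints are tempting but do not hold. Pain-only subjects without edema do not dilute the edema columns, because the Level 2 display separates reasons for enrollment. Having lymphedema in the pitting list is not in itself an analysis error, because the SAP counts these categories and never scores them as an ordered scale.

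**Conclusion.** The point holds for the scale as the SAP specifies it. Complete resolution has no level at baseline, interim or end of treatment, and each available way of entering it understates edema benefit. It should be fixed; confidence is moderate, subject to the form check.

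Only the direction is supported. The percentages above rest wholly on assumed baseline grades, resolution rates and one-level improvement, and route C also assumes that no interim grade had already improved.

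A reader might infer more than the documents allow:

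- That every full responder drops out of the final table. The last-recorded-value rule keeps those with an earlier follow-up grade, under that grade.
- That the bias can be stated as a mean change in grade. SAP 10.3.1 plans counts and percentages for categorical data, and no mean edema grade is specified.
- That edema is half of the study objective. Protocol Section II pairs pain with edema, but the objective in the protocol synopsis and in SAP 3.1 refers only to patients with various pain etiologies.

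**What to change.** 1. Check whether the case report form already offers a none or resolved option, or an edema-present item. If it does, only the SAP needs changing.
2. If not, add 'None' to the amount item and 'Not applicable (no edema)' to the pitting item at baseline, interim and end of treatment.
3. State in SAP 10.2.1 and 10.3.1 that resolved cases are counted as 'None' in Tables 14.4.1.3 and 14.4.2.3.
4. Among subjects with edema at baseline, report the proportion resolved and a shift table from baseline to last visit, with missing shown separately.

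The cost is a small form change, a few lines of SAP text and one added display. Subjects already assessed on the old categories must be flagged, because a Mild or blank entry for them may conceal a resolution.
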